### Description of DEMQOL and DEMQOL-Proxy:

The DEMQOL is a 28-item scale and DEMQOL-Proxy is a 31-item scale. All items are given a score from 1 to 4 (1 = a lot, 2 = quite a bit, 3 = a little, and 4 = not at all) and summed to produce total score and domain scores (daily activities, memory, negative emotion and positive emotion). However, large score indicates improvement for some items and deterioration for other items. In order to produce total score and domain scores such that a large score indicates improvement, the item score assuming large is deteriorating has to be reversed using the formula: new item score = (5 – current item score) or missing if the current item score is missing. The item score needs to be reversed for the following items:

DEMQOL: item1, item3, item5, item6, and item10;

DEMQOL-Proxy: item1, item4, item6, item8, and item11.

The missing item score will be imputed using developer's algorithm as described in developer's SPSS syntax ([Appendix 13.2](#)), i.e., if the number of missing item score for any subject is less than 15, then any missing item score will be imputed by subject's mean item score based on non-missing items; otherwise, the missing item score is still missing and the corresponding domain score and overall score is missing.

The responses for general quality of life item (very good, good, fair and poor) within DEMQOL and DEMQOL-Proxy are unscored and will be analyzed as ordinal response using GLMM.

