### 5.1.3 Exploratory Endpoint(s)

- Change from baseline at 12 weeks of treatment in the following endpoints:
  - SCOPA-Sleep total score and subscores
- Change from baseline at 12 weeks of treatment in the following endpoints:
  - Total score and domain scores of the DEMQOL and DEMQOL-Proxy
  - EQ-5D utility score and EQ-5D health status rating
- Percentage change from baseline in CSF cGMP concentrations after 9 weeks of treatment
- CIBIC-plus sub-items (Attention, Orientation, Memory, etc) rating

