## **8.4 Algorithms for Safety Parameters**

UPDRS-III subscores are defined as follows:

Tremor: sum of MDS-UPDRS-III category 3.15 to 3.18 (sum of 10 items from 4 categories: 3.15 Postural Tremor of the Hands, 3.16 Kinetic Tremor of the Hands, 3.17 Rest Tremor Amplitude, 3.18 Constancy of Rest Tremor).

Rigidity: sum of MDS-UPDRS-III category 3.3 (sum of 5 items from 1 category: 3.3 Rigidity).

Bradykinesia: sum of category 3.4 to 3.8 and 3.14 (sum of 11 items from 6 categories: 3.4 Finger Tapping, 3.5 Hand Movements, 3.6 Pronation-Supination Movements of Hands, 3.7 Toe Tapping, 3.8 Leg Agility, 3.14 Global Spontaneity of Movement [Body Bradykinesia]).

Postural instability and gait difficulty (PIGD): sum of category 3.9 to 3.13 (sum of 5 items from 5 categories: 3.9 Arising from Chair, 3.10 Gait, 3.11 Freezing of Gait, 3.12 Postural Stability, 3.13 Posture).

DEMQOL subscores are defined as follows:

Daily activities contains items 20 to 28, memory contains items 14 to 19, negative emotion contains items 2, 4, 7, 8, 9, 11, 12 and 13 and positive emotion contains items 1, 3, 5, 6, and 10.

DEMQOL-Proxy subscores are defined as follows:

Daily activities contains items 21 to 31, memory contains items 12 to 20, negative emotion contains items 2, 3, 5, 7, 9 and 10 and positive emotion contains items 1, 4, 6, 8, and 11.

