### APPENDIX 13.2.2 SPSS Syntax File for DEMQOL-Proxy

\*\*\*SPSS SYNTAX FILE FOR RECODING DEMQOL-PROXY DATA - JUNE 2005\*\*\*

\*\*\*DO NOT MODIFY\*\*\*

\*\*\*\*\*

\*\*\*RAW DATA SHOULD BE ENTERED AS FOLLOWS:

\*\*\*A LOT = 1; QUITE A BIT = 2; A LITTLE = 3; NOT AT ALL = 4

\*\*\*\*\*

\*\*\*\*

\*\*\*CREATE A SEPARATE FILE FOR EACH TIME POINT (EG BASELINE, 6  
MONTHS AND 12

\*\*\*MONTHS) AND CODE IT UP SEPARATELY.

\*\*\*IF YOU WANT TO MERGE THE FILES TOGETHER AFTER CODING, SO AS TO  
LOOK AT

\*\*\*CHANGE OVER TIME, YOU WILL NEED TO

\*\*\*RENAME THE 6 MONTH AND 12 MONTH SCORES TO INDICATE WHICH TIME  
THEY ARE

\*\*\*FROM (EG CDEMTOT\_S AND CDEMTOT\_T).

\*\*\*BUT DO NOT DO THIS UNTIL YOU HAVE FULLY SCORED AND CODED THE  
DATA USING

\*\*\*THE SYNTAX GIVEN HERE

\*\*\*\*\*

\*\*\*CODING SYNTAX

\*\*\*\*\*

\*\*\*1. CHANGE VARIABLE NAMES SO THAT: QUESTION 1 = CDEM1, QUESTION 2 = CDEM2,

\*\*\*QUESTION 3 = CDEM3 ETC FOR CARER VERSION

\*\*\*THEN CHECK THAT -99 IS SET AS THE MISSING VALUE

\*\*\*\*\*  
\*\*\*\*\*  
\*\*

\*\*\*2. RECODE ALL THE POSITIVE ITEMS FOR DIRECTION, SO THAT

\*\*\*FOR ALL ITEMS A HIGHER SCORE MEANS BETTER HRQL

\*\*\*\*\*  
\*\*\*

\*\*\*TO RECODE FOR DIRECTION OF ITEMS IN CARER DEMQOL\*\*\*

RECODE cdem1 cdem4 cdem6 cdem8 cdem11 cdem32 (1=4) (2=3) (3=2) (4=1).

EXECUTE.

\*\*\*\*\*  
\*\*\*\*

\*\*\*3. TO IMPUTE MISSING DATA >=50% FOR ONLY THE 31 ITEMS IN MAIN INSTRUMENT,

\*\*\*EXCLUDING THE GLOBAL QUESTION (#32)

\*\*\*\*\*  
\*\*\*\*

COMPUTE missall = NMISS (cdem1, cdem2, cdem3, cdem4, cdem5, cdem6, cdem7, cdem8,

cdem9, cdem10, cdem11,

cdem12, cdem13, cdem14, cdem15, cdem16, cdem17, cdem18, cdem19, cdem20, cdem21,

cdem22, cdem23, cdem24,

cdem25, cdem26, cdem27, cdem28, cdem29, cdem30, cdem31).

EXECUTE.

```
COMPUTE meanall = MEAN (cdem1, cdem2, cdem3, cdem4, cdem5, cdem6, cdem7,  
cdem8,  
cdem9, cdem10, cdem11,  
cdem12, cdem13, cdem14, cdem15, cdem16, cdem17, cdem18, cdem19, cdem20, cdem21,  
cdem22, cdem23, cdem24,  
cdem25, cdem26, cdem27, cdem28, cdem29, cdem30, cdem31).
```

EXECUTE.

```
IF (MISSING (cdem1) & missall < 16) cdem1 = meanall .
```

EXECUTE .

```
IF (MISSING (cdem2) & missall < 16) cdem2 = meanall .
```

EXECUTE .

```
IF (MISSING (cdem3) & missall < 16) cdem3 = meanall .
```

EXECUTE .

```
IF (MISSING (cdem4) & missall < 16) cdem4 = meanall .
```

EXECUTE .

```
IF (MISSING (cdem5) & missall < 16) cdem5 = meanall .
```

EXECUTE .

```
IF (MISSING (cdem6) & missall < 16) cdem6 = meanall .
```

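### SAP 5.7 applies a total-score imputation rule to the DEMQOL domain scores, so daily activities can be scored from no daily-activity answer; its Proxy limit also differs from the appended syntax

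*SAP*

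**What the plan says.** SAP 5.1.3 lists as exploratory endpoints the change from baseline at 12 weeks in "Total score and domain scores of the DEMQOL and DEMQOL-Proxy". SAP 5.7 analyses these by ANCOVA or GLMM, with multiple imputation under MAR for missing scores.

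In the scale description in SAP 5.7, "The DEMQOL is a 28-item scale and DEMQOL-Proxy is a 31-item scale", and item scores of 1 to 4 are "summed to produce total score and domain scores (daily activities, memory, negative emotion and positive emotion"). The missing-item rule is attributed to the developer's syntax in Appendix 13.2: "if the number of missing item score for any subject is less than 15, then any missing item score will be imputed", and the missing item is "imputed by subject's mean item score based on non-missing items". The alternative branch reads "otherwise, the missing item score is still missing and the corresponding domain score and overall score is missing". So a domain becomes missing only when the whole-scale count fails. Nothing is said about how many of a domain's own items must be answered, and no separate limit is given for the Proxy.

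SAP 8.4 assigns the items. For DEMQOL, "Daily activities contains items 20 to 28, memory contains items 14 to 19", and the emotion items lie among items 1 to 13. For the Proxy, daily activities is items 21 to 31, memory is 12 to 20, and emotion is 1 to 11.

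The Appendix 13.2 syntax averages all 28 or 31 items, fills the missing ones, and then computes one overall score per instrument. It contains no domain score. Its Proxy limit is 16: "IF (MISSING (cdem1) & missall < 16) cdem1 = meanall".

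**The concern.** For a total score, filling gaps with the subject's own item mean only scales up the answered part. For a domain score the same step can replace the domain's content with other content. An empty domain receives answers about mood and memory, and the result is labelled daily activities.

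The filled value also counts as observed. The multiple imputation in SAP 5.7 therefore never treats it as missing, and its uncertainty is not carried into the standard error.

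The SAP is stricter for its other scales. Under SAP 8.3, NPI-4 and NPI-10 are missing if any one of their items is missing, an MMSE domain with missing data is missing, and the MoCA total is missing if any assessment is missing. No reason is given for treating the DEMQOL domains differently.

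At stake is the meaning of an exploratory domain result. No success criterion depends on it.

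**Working it through.** **Inputs.** Item counts of 28 and 31, the 1-to-4 item range and the limit of 15 are from SAP 5.7. The domain item lists are from SAP 8.4. The syntax limits of 15 (DEMQOL) and 16 (Proxy) are from Appendix 13.2.

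**1. Reproduce the limit.** The syntax comments describe a 50% rule.
- DEMQOL: at least 14 of 28 answered means at most 28 - 14 = 14 missing, which is fewer than 15. This agrees with SAP 5.7 and with the DEMQOL syntax.
- Proxy: half of 31 is 15.5, so at least 16 answered means at most 31 - 16 = 15 missing, which is fewer than 16. This agrees with the Proxy syntax but not with the 15 in SAP 5.7. A Proxy form with exactly 15 items missing is scored by the syntax and is missing under the text.

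**2. Check that the domains cover each scale** (daily activities + memory + negative emotion + positive emotion).
- DEMQOL: 9 + 6 + 8 + 5 = 28.
- Proxy: 11 + 9 + 6 + 5 = 31.

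**3. Stop the interview just before daily activities.**

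| | DEMQOL | Proxy |
|---|---|---|
| Last item answered | 19 | 20 |
| Items missing | 28 - 19 = 9 | 31 - 20 = 11 |
| Below the limit? | 9 < 15, yes | 11 < 15 and < 16, yes |
| Daily-activity items answered | 0 of 9 | 0 of 11 |
| Daily-activities score | 9 x mean of 19 emotion and memory answers | 11 x mean of 20 emotion and memory answers |

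The earliest DEMQOL stop that still triggers imputation is after item 14 (14 missing). Daily activities then rests on 0 of 9 own items and memory on 1 of 6.

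**4. Size for one form.** Let m be the mean of the answered emotion and memory items, and d the true mean of the daily-activity items.
- DEMQOL error = 9 x (m - d), on a range of 36 - 9 = 27 points.
- Proxy error = 11 x (m - d), on a range of 44 - 11 = 33 points.

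The documents give no item means. I assume m from 2.0 to 3.5 and d from 1.5 to 3.5.

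| m | d | DEMQOL imputed | DEMQOL true | Error | % of range |
|---|---|---|---|---|---|
| 3.5 | 1.5 | 31.5 | 13.5 | +18.0 | +67% |
| 3.0 | 1.5 | 27.0 | 13.5 | +13.5 | +50% |
| 3.0 | 3.0 | 27.0 | 27.0 | 0 | 0% |
| 3.0 | 3.5 | 27.0 | 31.5 | -4.5 | -17% |
| 2.0 | 3.5 | 18.0 | 31.5 | -13.5 | -50% |

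The Proxy extremes are 11 x 2.0 = +22 and 11 x (-1.5) = -16.5 points, the same percentages of its range.

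**5. From one form to the treatment comparison.** This would need the number of interrupted interviews in each arm and the sign of m - d in those subjects. The documents give neither, so no effect on the treatment difference is computed.

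**6. After the change proposed under fix.** A half-answered rule within the domain needs 5 of 9 (DEMQOL) or 6 of 11 (Proxy) items. With 0 answered, daily activities is missing and goes to the multiple imputation.

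**The case against.** The case for leaving the text alone has four parts.

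- **Frequency.** Both instruments are administered by an interviewer at two visits (Protocol 9.5.1.6.1), and nothing in the documents says that interviews stop before the last block. A subject who progresses to severe dementia gets only the Proxy, which removes one foreseeable cause of incomplete DEMQOL forms. This stands as a limit on importance. Partial interviews are still plausible: for the co-primary endpoints, SAP 5.4.1 itself foresees assessments not done because the subject is drowsy, delirious or unwilling.
- **Developer's rule.** The syntax files are marked as not to be altered. That protects the overall score, which is all they compute. It gives no authority for the domains.
- **Remedy.** The half-of-domain threshold appears nowhere in the documents, and MI under MAR is itself an assumption that may fail if interviews stop through fatigue. Both are true. But the present rule assumes, without saying so, that the unanswered domain has exactly the mean of the others, with no uncertainty.
- **15 against 16.** Because SAP 5.7 defers to the appendix, its 15 can be read as a loose paraphrase. The difference affects only Proxy forms with exactly 15 missing items. It is small, but text and code cannot both be followed for such a form.

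A reader might also infer that an early stop empties the positive-emotion domain. It cannot. Those items are numbered 1, 3, 5, 6 and 10 (DEMQOL) and 1, 4, 6, 8 and 11 (Proxy), interleaved with negative emotion at the start. Only memory and daily activities are consecutive blocks.

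**Conclusion.** The rule as written is wrong for domain scores. It allows a daily-activities score with 0 of 9 (DEMQOL) or 0 of 11 (Proxy) of its own items answered, and treats that score as observed. This follows from the SAP's own text and item lists and needs no assumption. The per-form error of -13.5 to +18 DEMQOL points rests on assumed item means and shows extremes for one form at one visit.

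The SAP 5.7 limit of 15 also contradicts the Proxy syntax limit of 16.

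The point is minor. The endpoints are exploratory, and the number of affected subjects and the direction of bias are unknown. Two stronger conclusions are not supported. One is that a treatment effect on daily function would be hidden; the documents show only that this is possible. The other is that DEMQOL is the trial's sole patient- or caregiver-reported outcome, or its sole functional measure. EQ-5D and its proxy, NPI and CFI are also reported by subject or caregiver, EQ-5D asks about self-care and usual activities, and CIBIC-Plus covers activities of daily living.

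**What to change.** In SAP 5.7:

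- Keep the developer's whole-scale rule for the total scores only. State the limits separately, fewer than 15 missing for DEMQOL and fewer than 16 for DEMQOL-Proxy, as in Appendix 13.2.
- For each domain, fill missing items from the mean of that domain's own answered items when at least half are answered. Otherwise set the domain score to missing and leave it to the MI already planned. The half threshold is a proposal that extends the developer's 50% rule to the domain; it is not taken from the documents.
- Compute domain scores from the items before whole-scale filling, because the syntax overwrites the item values.

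The cost is a few lines of SAP text and scoring code, with no new data. Slightly more domain scores will be missing. In subjects with imputed items the domain scores may no longer sum to the total, which should be stated in the SAP and in the table footnotes.

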## 13.2 SPSS Syntax Files for DEMQOL and DEMQOL-Proxy

The SPSS syntax files present the developer's algorithm to handle the missing item score in DEMQOL and DEMQOL-Proxy.

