### APPENDIX 13.2.1 SPSS Syntax File for DEMQOL

\*\*\*SPSS SYNTAX FILE FOR RECODING PWD DEMQOL DATA - JUNE 2005 \*\*\*

\*\*\*DO NOT MODIFY\*\*\*

\*\*\*\*\*

\*\*\*RAW DATA SHOULD BE ENTERED AS FOLLOWS:

\*\*\*A LOT = 1; QUITE A BIT = 2; A LITTLE = 3; NOT AT ALL = 4

\*\*\*\*\*

\*\*\*\*

\*\*\*CREATE A SEPARATE FILE FOR EACH TIME POINT (EG BASELINE, 6 MONTHS AND 12

\*\*\*MONTHS) AND CODE IT UP SEPARATELY.

\*\*\*IF YOU WANT TO MERGE THE FILES TOGETHER AFTER CODING, SO AS TO LOOK AT

\*\*\*CHANGE OVER TIME, YOU WILL NEED TO

\*\*\*RENAME THE 6 MONTH AND 12 MONTH SCORES TO INDICATE WHICH TIME THEY ARE

\*\*\*FROM (EG DEMTOT\_S AND DEMTOT\_T).

\*\*\*BUT DO NOT DO THIS UNTIL YOU HAVE FULLY SCORED AND CODED THE DATA USING

\*\*\*THE SYNTAX GIVEN HERE

\*\*\*\*\*

\*\*\*CODING SYNTAX

\*\*\*\*\*

\*\*\*1. CHANGE VARIABLE NAMES SO THAT: QUESTION 1 = DEM1, QUESTION 2 = DEM2,

\*\*\*QUESTION 3 = DEM3 ETC

\*\*\*THEN CHECK THAT -99 IS SET AS THE MISSING VALUE

\*\*\*\*\*  
\*\*\*\*\*  
\*\*

\*\*\*2. RECODE ALL THE POSITIVE ITEMS FOR DIRECTION, SO THAT

\*\*\*FOR ALL ITEMS A HIGHER SCORE MEANS BETTER HRQL

\*\*\*\*\*  
\*\*\*

\*\*\*TO RECODE FOR DIRECTION ITEMS IN THE PATIENT DEMQOL\*\*\*

RECODE dem1 dem3 dem5 dem6 dem10 dem29

(1=4) (2=3) (3=2) (4=1).

EXECUTE.

\*\*\*\*\*  
\*\*\*\*

\*\*\*3. IMPUTE MISSING DATA >=50% FOR ONLY THE 28 ITEMS THAT CONTRIBUTE TO

\*\*\*THE SCORE

\*\*\*IE EXCLUDING THE GLOBAL QUESTION (#29)

\*\*\*\*\*  
\*\*\*\*

COMPUTE missall= NMIS (dem1, dem2, dem3, dem4, dem5, dem6, dem7, dem8, dem9,  
dem10, dem11,  
dem12, dem13, dem14, dem15, dem16, dem17, dem18, dem19, dem20, dem21, dem22,  
dem23, dem24,

dem25, dem26, dem27, dem28).

EXECUTE.

COMPUTE meanall = MEAN (dem1, dem2, dem3, dem4, dem5, dem6, dem7, dem8, dem9,  
dem10, dem11,

dem12, dem13, dem14, dem15, dem16, dem17, dem18, dem19, dem20, dem21, dem22,

dem23, dem24,

dem25, dem26, dem27, dem28).

EXECUTE.

IF (MISSING (dem1) & missall < 15) dem1 = meanall .

EXECUTE .

IF (MISSING (dem2) & missall < 15) dem2 = meanall .

EXECUTE .

IF (MISSING (dem3) & missall < 15) dem3 = meanall .

EXECUTE .

IF (MISSING (dem4) & missall < 15) dem4 = meanall .

EXECUTE .

IF (MISSING (dem5) & missall < 15) dem5 = meanall .

EXECUTE .

IF (MISSING (dem6) & missall < 15) dem6 = meanall .

EXECUTE .

IF (MISSING (dem7) & missall < 15) dem7 = meanall .

EXECUTE .

IF (MISSING (dem8) & missall < 15) dem8 = meanall .

EXECUTE .

IF (MISSING (dem9) & missall < 15) dem9 = meanall .

EXECUTE .

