EXECUTE .

```
IF (MISSING (cdem7) & missall < 16) cdem7 = meanall .
```

EXECUTE .

```
IF (MISSING (cdem8) & missall < 16) cdem8 = meanall .
```

EXECUTE .

IF (MISSING (cdem9) & missall < 16) cdem9 = meanall .

EXECUTE .

IF (MISSING (cdem10) & missall < 16) cdem10 = meanall .

EXECUTE .

IF (MISSING (cdem11) & missall < 16) cdem11 = meanall .

EXECUTE .

IF (MISSING (cdem12) & missall < 16) cdem12 = meanall .

EXECUTE .

IF (MISSING (cdem13) & missall < 16) cdem13 = meanall .

EXECUTE .

IF (MISSING (cdem14) & missall < 16) cdem14 = meanall .

EXECUTE .

IF (MISSING (cdem15) & missall < 16) cdem15 = meanall .

EXECUTE .

IF (MISSING (cdem16) & missall < 16) cdem16 = meanall .

EXECUTE .

IF (MISSING (cdem17) & missall < 16) cdem17 = meanall .

EXECUTE .

IF (MISSING (cdem18) & missall < 16) cdem18 = meanall .

EXECUTE .

IF (MISSING (cdem19) & missall < 16) cdem19 = meanall .

EXECUTE .

IF (MISSING (cdem20) & missall < 16) cdem20 = meanall .

EXECUTE .

---

IF (MISSING (cdem21) & missall < 16) cdem21 = meanall .

EXECUTE .

IF (MISSING (cdem22) & missall < 16) cdem22 = meanall .

EXECUTE .

IF (MISSING (cdem23) & missall < 16) cdem23 = meanall .

EXECUTE .

IF (MISSING (cdem24) & missall < 16) cdem24 = meanall .

EXECUTE .

IF (MISSING (cdem25) & missall < 16) cdem25 = meanall .

EXECUTE .

IF (MISSING (cdem26) & missall < 16) cdem26 = meanall .

EXECUTE .

IF (MISSING (cdem27) & missall < 16) cdem27 = meanall .

EXECUTE .

IF (MISSING (cdem28) & missall < 16) cdem28 = meanall .

EXECUTE .

IF (MISSING (cdem29) & missall < 16) cdem29 = meanall .

EXECUTE .

IF (MISSING (cdem30) & missall < 16) cdem30 = meanall .

EXECUTE .

IF (MISSING (cdem31) & missall < 16) cdem31 = meanall .

EXECUTE .

\*\*\*\*\*

\*\*\*4. TO COMPUTE OVERALL DEMQOL -PROXY SCORE

\*\*\*NOTE THAT THE SCORE CONSISTS OF ITEMS 1-31 ONLY.

\*\*\*QUESTION 32 DOES NOT CONTRIBUTE TO THE SCORE

\*\*\*\*\*

COMPUTE cdemtot = cdem1 + cdem2 + cdem3 + cdem4 + cdem5 + cdem6 + cdem7 +  
cdem8 +

cdem9 + cdem10 + cdem11 +

cdem12 + cdem13 + cdem14 + cdem15 + cdem16 + cdem17 + cdem18 + cdem19 + cdem20  
+

cdem21 + cdem22 + cdem23 + cdem24 +

cdem25 + cdem26 + cdem27 + cdem28 + cdem29 + cdem30 + cdem31.

EXECUTE.

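### SAP 5.7 gives one missing-item limit (fewer than 15) for both DEMQOL and DEMQOL-Proxy, but the developer syntax it cites uses fewer than 16 for the 31-item DEMQOL-Proxy

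*SAP*

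**What the plan says.** The description of the two instruments in SAP 5.7 gives their lengths: "The DEMQOL is a 28-item scale and DEMQOL-Proxy is a 31-item scale". It then sets the missing-item rule for both by reference: "The missing item score will be imputed using developer's algorithm as described in developer's SPSS syntax". The paraphrase that follows has one condition, "if the number of missing item score for any subject is less than 15", under which the subject's mean over answered items is used. Failing that, "otherwise, the missing item score is still missing and the corresponding domain score and overall score is missing". No separate limit is given for the proxy form.

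The opening of Appendix 13.2 says that the files cover both instruments: "The SPSS syntax files present the developer's algorithm to handle the missing item score in DEMQOL and DEMQOL-Proxy". The DEMQOL file (13.2.1) has "IF (MISSING (dem1) & missall < 15) dem1 = meanall", and the same limit for all 28 items. The DEMQOL-Proxy file (13.2.2) has "IF (MISSING (cdem1) & missall < 16) cdem1 = meanall", and the same limit through to the last line, "IF (MISSING (cdem31) & missall < 16) cdem31 = meanall".

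**The concern.** The text and the source it cites give different rules for the proxy form, and the SAP neither acknowledges a departure nor says which takes precedence. The limit in the text matches the shorter scale. Elsewhere the SAP treats the two scales separately: 5.7 lists the reverse-scored items for each, and 8.4 lists the domain items for each. A single limit therefore looks like an oversight, not a choice.

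At stake is how one kind of proxy form enters the analysis. Under the syntax its total comes from the subject's own form. Under the text the total is missing and, at Week 12, 5.7 handles it by multiple imputation assuming MAR. SAP Section 10 specifies SAS, while the appendix is SPSS code, so the algorithm must be re-programmed. A programmer and an independent validator could each follow a different part of the SAP in good faith.

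**Working it through.** **Inputs.** Items: 28 for DEMQOL and 31 for DEMQOL-Proxy (SAP 5.7). Text rule for both: impute if m < 15, where m is the number of missing items (SAP 5.7). Syntax rule: m < 15 for DEMQOL (Appendix 13.2.1) and m < 16 for DEMQOL-Proxy (Appendix 13.2.2).

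**Step 1: does the text limit reproduce from the appendix?** For DEMQOL it does, 15 in both. For DEMQOL-Proxy it does not, 15 against 16.

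**Step 2: where do the rules differ?** Comparing them at every possible m:

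| Scale | Most missing items allowed, text | Most missing items allowed, syntax | Counts where they disagree |
|---|---|---|---|
| DEMQOL (28) | 14 (14/28 = 50.0%) | 14 (14/28 = 50.0%) | none |
| DEMQOL-Proxy (31) | 14 (14/31 = 45.2%) | 15 (15/31 = 48.4%) | m = 15 only |

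**Step 3: what happens at m = 15 on the proxy form?** There are 31 − 15 = 16 answered items, with sum S after reversal of the positively worded items.
- Syntax: 15 < 16 is true. Each missing item takes the value S/16, and the total is S + 15 × S/16 = 31S/16.
- Text: 15 < 15 is false. The missing items stay missing, and so does the total.

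**Step 4: domain scores.** The appendix syntax computes only the total. The proxy domains are defined in SAP 8.4, with 11 items for daily activities, 9 for memory, 6 for negative emotion and 5 for positive emotion (11 + 9 + 6 + 5 = 31). The text sets the corresponding domain scores to missing, so the conflict is clear for domains that contain a missing item. A domain answered in full can still be read as scorable under the text. This can occur at m = 15: with all 11 daily-activities items answered, 31 − 11 = 20 other items remain, enough to hold 15 missing.

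**Step 5: which limit fits the syntax's own comment?** The comment above the imputation step refers to 50%. Read as requiring at least half the items to be answered, it needs 14 of 28 (at most 14 missing) and 16 of 31 (at most 15 missing), because 31/2 = 15.5. These are the two limits in the syntax. This reading of a terse comment is an interpretation, and the disagreement in Step 2 does not depend on it.

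**Step 6: exposure.** Proxy forms are scheduled at Baseline and Day 84 (protocol 9.5.1.6.1). With 182 subjects planned, that is at most 182 × 2 = 364 scheduled forms, of which only those with exactly 15 missing items are affected. The documents give no item-missingness rate, so the number cannot be calculated. None or very few is an assumption, though a plausible one for an interview-administered scale.

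**The case against.** The strongest reply is that the syntax already governs. Section 5.7 makes it the source of the algorithm, the figure of 15 appears only in the paraphrase, and the proxy file is printed in full under a heading that tells users not to change it. On that reading the paraphrase is merely incomplete. SAP Section 9 also places programming rules in separate documents, so the rule actually coded may already be 16. This is a fair reading and perhaps the likelier intention, and it limits what can be claimed. It does not remove the error: the paraphrase is an explicit rule under a heading covering both scales, and it is wrong for one of them.

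Three stronger inferences are tempting, and the documents support none of them:
- That the trial will in fact apply the DEMQOL limit to proxy forms. The documents show only that the text permits it.
- That the text departs from a validated scoring rule. The SAP calls the algorithm the developer's and does not describe the missing-item rule as validated.
- That every affected form would be replaced by multiple imputation. Section 5.7 specifies this for the change at 12 weeks and does not say how a missing baseline proxy score is handled in the ANCOVA.

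**Conclusion.** Wrong as written, as an internal inconsistency; a minor correction that is worth making. For DEMQOL-Proxy the limit in 5.7 does not match the syntax it cites, and the two give different results at exactly one count, 15 of 31 items missing. The difference is certain for the total and for domains containing missing items. The practical effect is very small: DEMQOL-Proxy is exploratory, and no primary or secondary efficacy result, significance level or power figure changes. The inconsistency can be read directly from the SAP without any assumption; only the expectation that few forms are affected is assumed.

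**What to change.** In SAP 5.7, replace the single limit with one per scale: fewer than 15 missing of 28 items for DEMQOL, and fewer than 16 missing of 31 items for DEMQOL-Proxy, as in Appendix 13.2. Text and syntax then agree at every count of missing items. The cost is one phrase, with no effect on trial conduct, data collection or any other analysis. It is best done before unblinding, so that no scoring decision is made with treatment groups in view, and the programming specification should be checked for the same limits.
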